RESEARCH QUESTION AND OBJECTIVES:	
The aim of this study is to evaluate the awareness, knowledge, and adherence of prescribers and patients/carers to the additional Risk Minimisation Measures (RMM) for Hemlibra®.
 
Prescriber (HCP) survey
 
 ○ Assess prescriber awareness of the Hemlibra® educational program ● Assess prescriber knowledge of: 
 ○ the identified risks (Thrombotic microangiopathy [TMA] and thrombotic events [TEs]) ○ the potential risk of life-threatening bleeding due to misinterpretation of the standard coagulation tests ● Assess prescriber self-reported adherence to the additional RMMs 
Patient/carer survey
 
 ● Assess patient/carer awareness of the Hemlibra® educational program ● Assess patient/carer knowledge of: 
 ○ the identified risks of TMA and TE ○ the potential risk of life-threatening bleeding due to misinterpretation of the standard coagulation tests ● Assess patient/carer self-reported adherence to the additional RMMs

COUNTRIES OF STUDY POPULATION:	UK, Italy, Germany, Spain, France, Belgium, Netherlands, Poland, Austria, Portugal, Czech Republic, Hungary, Romania
MARKETING AUTHORIZATION HOLDER (MAH):	Roche Registration GmbH [name]
MAH CONTACT PERSON:	Dr. [REDACTED] EU Product Development Regulatory Phone: [REDACTED] Fax: [REDACTED] Email: [REDACTED]

PROTOCOL HISTORY

Protocol	
Version	Date Final
1	(not approved)
2	27 March 2019

PROTOCOL AMENDMENT, VERSION 3:

RATIONALE

Version 3 of protocol BO40853 has been amended from Version 2 primarily to extend timelines for study conduct to enable the collection of a sufficient number of completed HCP and patient questionnaires across different European regions to ensure representativeness and fulfil the planned data analysis. Version 2 of the protocol was the first version approved by PRAC. The changes to the protocol, along with the rationale for each change, are summarized below:

- The aim of this survey study is to evaluate the awareness, knowledge, and adherence of prescribers (HCPs) and patients/carers to the additional risk minimisation measures (aRMMs) for Hemlibra®. A sample size of 40 HCPs and 70 patients were planned to be surveyed in three European geographic regions. As of the 28th of July 2020, 107 HCPs and 46 patients have completed the respective questionnaires, with a majority of respondents coming from Northern and Western Europe. The number of completed patient questionnaires obtained thus far is smaller than planned and their distribution across the surveyed EU countries is not balanced. The PRAC Rapporteur has requested to extend data collection by 3 months. Consequently, the end of data collection date in the protocol has been moved from Q3 2020 to Q4 2020 (end December 2020) and the availability of the final study report has been moved to Q3 2021 (Section 4; 5; 8.1 and 8.4.2).
- The possibility to recruit patients and carers through HCPs who have not completed the HCP Questionnaire has been added to the protocol. As per the initial protocol, HCPs who have completed the HCP Questionnaire were offered to share Patients Questionnaire and Carer Questionnaire with their patients treated with Hemlibra®, or their carers, respectively. During submission of the protocol to ethics committees in some of the participating countries, lead physicians were provided with the protocol and HCP Questionnaire, which has made them ineligible for participation in the study. In fact, prior exposure would cause an information bias due to the pre acknowledgement of a number of facts that we are asking in the survey. Consequently, access to the patients of these physicians was impeded which had an impact on Patient and Carer Questionnaires data collection. In order to compensate for the loss of patients caused by the above, the protocol has been modified to allow HCPs to share the Questionnaires with patients/carers without prior requirement for HCPs to complete the HCP Questionnaire (Section 8.1; 8.1.1; 8.4.1 and 8.5.2).
- Geographic grouping of countries was originally suggested as the main criterion for grouping for the analysis. The statistical analysis section (Section 8.7.1) was updated to allow for other criteria of grouping which may also be used for results presentation e.g., Euro Health Consumer Index. The Euro Health Consumer Index is a commonly used index for assessing the performance of national health systems and it enables grouping of countries based on quality of healthcare as assessed by patients. In addition, the section about analysis of

response rate (Section 8.7.3) was updated to match the Statistical Analysis Plan and reflect the actual various groupings that result from the recruitment operations (see Section 8.4.1).

Additional minor changes, including updates in administrative information, have been made to improve clarity and consistency. Substantive new information appears in italics. This amendment represents cumulative changes to the original protocol.

1. **TABLE OF CONTENTS**

PROTOCOL HISTORY	4
PROTOCOL AMENDMENT, VERSION 3:	5
RATIONALE	5
1. TABLE OF CONTENTS	7
LIST OF TABLES	9
LIST OF ABBREVIATIONS	10
2. RESPONSIBLE PARTIES	11
3. SYNOPSIS.....	12
4. PROTOCOL AMENDMENTS AND UPDATES	17
5. MILESTONES.....	17
6. RATIONALE AND BACKGROUND.....	18
6.1 Study Rationale	18
6.2 Study Background	20
7. RESEARCH QUESTION AND OBJECTIVES.....	20
7.1 Research Question	20
7.2 Objectives.....	21
8. RESEARCH METHODS	22
8.1 Study Design	22
8.1.1 Rationale for Study Design	22
8.2 Setting	22
8.2.1 Countries	23
8.2.2 Study Population	23
8.2.3 Concomitant Medication and Treatment.....	24
8.2.4 Dosage, Administration, and Compliance.....	24
8.3 Variables.....	24
8.4 Data Sources.....	26
8.4.1 Identification of HCPs and Patients	26

8.4.2	Data Collection	26
8.4.3	Data Collected at Study Completion.....	28
8.5	Study Size	29
8.5.1	Study Size Calculation.....	29
8.5.2	Sampling Plan	30
8.5.3	Sample Adjustment	31
8.6	Data Management	31
8.6.1	Data Quality Assurance	31
8.6.2	Source Data Documentation.....	32
8.7	Data Analysis.....	32
8.7.1	General Considerations	33
8.7.2	Planned Analyses	34
8.7.3	Analysis of Response Rate	34
8.7.4	Questionnaire Analysis	35
8.7.5	Handling of Missing Data	37
8.8	Quality Control.....	38
8.8.1	Study Documentation	38
8.8.2	Site Audits and Inspections	39
8.8.3	Safeguards, Security and Traceability of Contacts	39
8.8.4	Retention of Records.....	40
8.9	Limitations of the Research Method	40
8.10	Other Aspects.....	42

3. SYNOPSIS

TITLE:	HEMLIBRA SURVEY TO PRESCRIBERS AND PATIENTS/CARERS TO EVALUATE AWARENESS, KNOWLEDGE AND COMPLIANCE TO ADDITIONAL RISK MINIMISATION MEASURES
PROTOCOL NUMBER:	BO40853
VERSION NUMBER:	3.0
DATE OF SYNOPSIS:	See electronic stamp on the cover page
EU PAS REGISTER NUMBER:	EUPAS30451
STUDIED MEDICINAL PRODUCT:	Hemlibra®
SCIENTIFIC RESPONSIBLE	██████████, Genentech
MAIN AUTHOR	██████████, F. Hoffmann-La Roche
PHASE:	IV, non-interventional study
INDICATION:	For routine prophylaxis of bleeding episodes in patients with haemophilia A with factor VIII inhibitors and patients with severe haemophilia A without factor VIII inhibitors
MARKETING AUTHORIZATION HOLDER:	Roche Registration GmbH [name]

Rationale and Background

Hemlibra® (Emicizumab) is a humanized bispecific antibody targeting factors IX (FIX) and X (FX). In patients with haemophilia A, Hemlibra® bridges activated FIX and FX to restore the function of missing activated factor VIII (FVIII) that is needed for effective haemostasis. Hemlibra® received a marketing authorisation valid throughout the European Union (EU) on 23 February 2018 for the indication: routine prophylaxis of bleeding episodes in patients of all age groups with haemophilia A with FVIII inhibitors. On 31 January 2019, the Committee for Medicinal Products for Human Use (CHMP) adopted a favourable opinion on the expansion of the indication of Hemlibra® to patients of all age groups with severe haemophilia A without FVIII inhibitors. In patients with haemophilia A receiving Hemlibra®, concomitant use of activated prothrombin complex concentrate (aPCC) averaging a cumulative amount of >100U/kg/24 hours for 24 hours or more is associated with the following important identified risks: thrombotic microangiopathy [TMA] and thromboembolic events [TEs]). In addition, an important potential risk is life-threatening bleeding due to misinterpretation of the standard coagulation tests, which are unreliable in patients treated with Hemlibra®. To manage these risks, additional Risk Minimisation Measures (RMMs), including the following educational materials were developed: healthcare professional guide, patient/carer guide and patient alert card. To assess prescribers' (health care providers [HCPs]) and patients' or their carers' awareness of the Hemlibra® educational program, knowledge of identified and potential life-threatening risks associated with Hemlibra® use, and adherence to additional RMMs Roche plans to conduct a non-interventional Post-Authorisation Safety Study in the form of a survey.

Research Question and Objectives

The aim of this study is to evaluate the awareness, knowledge, and adherence of prescribers and patients/carers to the additional RMMs for Hemlibra®.

Objectives

To evaluate whether prescribers and the patients/carers have understood the requirements of and report adherence with the additional RMMs associated with Hemlibra®. The objectives of the study are as follows:

Prescriber (HCP) survey

- Assess prescriber awareness of the Hemlibra® educational program by evaluating the proportion of targeted prescribers who acknowledge having received and read the relevant educational materials.
- Assess prescriber knowledge of:
 - the important identified risks of TMA and TEs that may occur if a cumulative amount of >100U/kg/24 hours for 24 hours or more of aPCC is used concomitantly with Hemlibra® by patients and
 - the important potential risk of life-threatening bleeding due to misinterpretation of the standard coagulation tests, which may be unreliable in patients treated with Hemlibra®,by evaluating the proportion of targeted prescribers with correct responses to risk knowledge questions.
- Assess prescriber adherence to the additional RMMs, by evaluating the proportion of targeted prescribers whose responses to the practice-related questions are consistent with the Guide for Healthcare Professionals.

Patient/carer survey

- Assess patient/carer awareness of the Hemlibra® educational program by evaluation the proportion of patients who acknowledge having received and read the Patient/Carer Guide and Patient Alert Card.
- Assess patient/carer knowledge of:
 - the important identified risks of TMA and TEs that may occur if a cumulative amount of >100U/kg/24 hours for 24 hours or more of aPCC is used concomitantly with Hemlibra® by patients and

- the important potential risk of life-threatening bleeding due to misinterpretation of the standard coagulation tests, which may be unreliable in patients treated with Hemlibra®,

by evaluating the proportion of patients/carers with correct responses to risk knowledge questions.

- Assess patient/carer adherence to the additional RMMs, which will be evaluated by evaluating the proportion of patients/carers whose responses to questions are consistent with the Patient/Carer Guide and Patient Alert Card.

Study Design

The study will utilize anonymous, cross-sectional, multi-national, surveys conducted among HCPs and patients or carers in 13 European countries, using primary data collection in the form of online questionnaires.

Description of Study

The study will be conducted between Q1 and Q4 2020. The surveys to prescribers (HCP) and patients/carers will assess their awareness of the Hemlibra® educational program, knowledge of important identified risks (TMA and TEs) and important potential life-threatening risk of bleeding due to misinterpretation of the standard coagulation tests associated with Hemlibra® use, and adherence to additional RMMs. To ensure that only relevant HCPs are targeted, the survey will only include HCPs that have treated haemophilia patients with Hemlibra® outside of clinical trials at least once. Patients or their carers will be recruited via *their* physicians. The questionnaires will include multiple-choice and closed-ended questions as appropriate. The surveys will be conducted in a web-based format as a standard for both HCPs and patients/carers and guided by phone if preferred by the participating HCPs.

Population

The study population is HCPs who have prescribed Hemlibra® outside of the clinical trials and patients with haemophilia A who have been or are currently being treated with Hemlibra®, both of whom must meet the following inclusion/exclusion criteria:

Inclusion

HCPs

- HCPs who prescribed Hemlibra® at least once outside the context of a clinical trial to patients with haemophilia A with FVIII inhibitors or patients with severe haemophilia A without FVIII inhibitors
- HCPs who are willing to participate in this survey

Patients/Carers

- Patients who received at least 4 doses of Hemlibra® within the last 6 months, including patients on ongoing therapy, or their carers
- Patients who are willing to participate in this self-administered survey, or their carers (parent or legal guardian) if the patient is under the age of 18

Exclusion

HCPs

- HCPs who may have conflicts of interest with the study (e.g., HCPs employed by Roche or IQVIA)

Patients/Carers

- Patients/carers who may have conflicts of interest with the study (e.g., patients/carers employed by Roche or IQVIA)
- Patients who have participated in a Hemlibra® clinical trial
- Patients with non-severe haemophilia A without FVIII inhibitors

Variables

Prescriber (HCP) survey

- Variables related to HCP participation
 - Response rate
 - Refusal rate
- Variables related to HCP practice information:
 - Location (city/country)
 - HCP primary specialization
 - Years practicing as a physician
 - Practice setting (Haemophilia Comprehensive Care Centre, haemophilia treatment centre, hospital haematology department, other)
 - Past experience with Hemlibra® (overall number of patients, number of patients with inhibitors, and severe patients without inhibitors treated)
 - Participation as a Hemlibra® clinical trial investigator
 - Last time prescribing Hemlibra®
 - Makeup of patient population (adults or children)
- Variables related to HCPs' awareness of the Hemlibra® educational program
 - Receipt of each of the RM tools (Patient Alert Card, Patient/Carer Guide, Guide for Healthcare Professionals) (yes/no)
 - Reading of the Guide for Healthcare Professionals (yes/no)
- Variables related to the HCPs' knowledge of the risks associated with the use of Hemlibra®, as described in the educational materials:
 - Knowledge of guidelines on the use of bypassing agents in their patients receiving Hemlibra® prophylaxis, particularly for TMA and TE with concomitant aPCC use (true/false statements)
 - Knowledge of laboratory coagulation tests which have their reliability affected by Hemlibra® and associated recommendations (tick boxes with answers that are either consistent or inconsistent with the additional RMMs)
 - Knowledge of time period to follow dosing and laboratory testing guidelines (tick boxes with answers that are either consistent or inconsistent with the additional RMMs)
- Variables related to the HCPs' self-reported adherence to the educational measures by correct implementation of the additional RMMs:
 - Distribution of Patient Alert Cards and Patient/Carer Guides to patients receiving Hemlibra® prophylaxis (or their carers) (tick boxes listing frequency of distribution of RM tools to patients)
 - Counselling of patients or their carers to carry the Patient Alert Card for 6 months after their last dose of Hemlibra (tick boxes with answers that are either consistent or inconsistent with the additional RMMs)
 - Use of activated partial thromboplastin time (aPTT) test results in patient who receive Hemlibra® (yes/no)
 - Precautions followed when prescribing Hemlibra® (tick boxes with answers that are either consistent or inconsistent with the additional RMMs)
 - Bypassing dosing guidance in their patients receiving Hemlibra® prophylaxis (tick boxes with answers that are either consistent or inconsistent with the additional RMMs)

Patient/carer survey

- Variables related to the patients treated with Hemlibra®:
 - Completion by patient or carer
 - Patient age (years)
 - Time since last dose of Hemlibra® (tick boxes with ranges of treatment duration in months)
 - Diagnosis with FVIII inhibitors (yes/no)
 - Severity of disease (mild/moderate/severe)

- Receiving at least 4 doses of Hemlibra® in the last 6 months (yes/no)
- Variables related to the patients' awareness of the Hemlibra® educational program, or the awareness of their carer if the patient is under the age of 18:
 - Receipt of Patient Alert Card and Patient/Carer Guide (tick boxes for receipt)
 - Discussion with HCPs of risks associated with the use of Hemlibra® (yes/no)
 - Reading of the received educational materials (yes/no)
- Variables related to the patients' knowledge about the risks of Hemlibra®, or the knowledge of their carer if the patient is under the age of 18:
 - Knowledge of risks associated with the use of Hemlibra® (tick boxes with answers that are either consistent or inconsistent with the additional RMMs)
 - Knowledge that the Patient Alert Card should be carried at all times (tick boxes with answers that are either consistent or inconsistent with the additional RMMs)
 - Knowledge that Hemlibra® use can affect laboratory tests on blood clotting (true/false)
 - Knowledge of aPCC dosing and risks of concomitant use with Hemlibra® therapy (true/false statements)
- Variables related to the patients' self-reported adherence to the educational measures by correct implementation of the additional RMMs, or the self-reported adherence of their carer if the patient is under the age of 18:
 - Showing the Patient Alert Card to health care professionals (yes/no)
 - For patients taking aPCC while taking Hemlibra®:
 - Taking a first dose of aPCC of <50U/kg
 - Contacting their HCP before increasing the dose of aPCC above 50U/kg (yes/no/not applicable)
 - Not taking >100U/kg/24 hours for 24 hours or more (yes/no)

Data Sources

The study is a survey using primary data collection conducted through HCP and patient/carer questionnaires administered online, with an option to be guided by phone for HCPs and is planned to be conducted in 13 European countries.

Study Size

A sample size of 40 HCPs will be surveyed. Since the response rate in some similar surveys has been as low as 10%, the questionnaire will be sent to at least 400 potential prescribers of Hemlibra in 13 European countries.

HCPs will be asked to distribute up to 18 survey kits to their patients or carers. Assuming 15-20% of HCPs agree to distribute the survey and that 20-40% of patients/carers respond, our target sample size is 70 patient questionnaires, including 25-35 from patients with inhibitors or their carers.

Data Analysis

The statistical analysis will be conducted using the SAS software V9.4 on Windows™ (SAS Institute, North Carolina, USA).

Results will be presented, overall and by geographic region. *Other criteria for grouping may also be used for results presentation e.g., Euro Health Consumer Index.* Continuous variables will be described by the number of valid cases and missing data (if applicable), mean, standard deviation, median, first quantile (Q1), third quantile (Q3), minimum, and maximum. No missing data will be imputed. Categorical variables will be described as the total number and relative percentage per category. Confidence intervals of 95% will be estimated when relevant.

Individual awareness, knowledge, and adherence values will be calculated as the percentage of correctly answered survey questions; values will range from 0 to 100% with 100% representing the percentage of all knowledge questions and behaviour questions being answered correctly, respectively.

Analysis will be done on questions common to all HCPs and patients/carers as well as on a limited number of questions presented to the subgroup of patients with concomitant use of aPCC (FEIBA) and Hemlibra® (or their carers).

Potential selection bias will be assessed by comparing the distributions of available characteristics (e.g. region, type of practice and speciality) between respondent and non-respondent HCPs, if applicable and feasible.

Success on the educational materials for additional risk minimisation measures will be defined a priori as achieving overall scores of $\geq 75\%$ for awareness and adherence and $\geq 60\%$ for knowledge for HCPs and $\geq 60\%$ in all areas for patients/carers. Overall success is defined as success on all three measures for both HCPs and patients/carers (see Section 8.7).

The planned analyses will be fully described in the Statistical Analysis Plan (SAP) to be developed after protocol approval by the European Medicines Agency (EMA).

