8. RESEARCH METHODS

8.1 STUDY DESIGN

The study will utilize cross-sectional, multinational, surveys conducted among prescribers (physicians) and patients or their carers in European countries in the form of online questionnaires.

The physician part of the survey will be conducted first. The physician will initially be contacted by email or phone calls. The survey will be conducted in a web-based format and guided by phone if the participating HCPs prefer it (see Section 8.4.2).

To conduct the patient/carer part of the survey, *contacted* HCPs will be asked to propose the online survey to their patients. *HCPs will be able to propose the online survey to their patients even if they have not participated in the HCPs survey.*

Start Date of Study

The anticipated study start date for the HCP survey is Q1 2020. The anticipated patient/carer survey start date is Q2 2020.

End of Study

The end of the study will be the date from which the last data collected from the last survey recorded in the study database. The anticipated study completion is Q4 2020.

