8.5 STUDY SIZE

8.5.1 Study Size Calculation

The sample size determination is based on the following sample size formula based on the normal approximation to the binomial:

$$n = \frac{P \cdot (1 - P) \cdot (Z_{1-\alpha/2})^2}{e^2},$$

where P is the expected proportion, e is one half the desired width of the confidence interval, and $Z_{1-\alpha/2}$ is the standard normal Z value corresponding to a cumulative probability of $1 - \alpha/2$ (e.g., if $\alpha = .05$ then $Z = 1.96$).

The proportions of interest (p) here are the proportions mentioned under specific objectives above. As p is not known in advance, we consider it to be 50% (maximum uncertainty). Such a hypothesis yields the most conservative, i.e., the largest, sample size. For example, the required sample size would be 43 for precision levels of 15%. [Table 2](#) provides precision of the estimate (width of 95% CI around the estimate) for a range of sample sizes.

Table 2 Precision of the Estimate for a Range of Sample Sizes

Sample Size	Statistical Precision (%)
43	±15
67	±12
80	±11
96	±10

Prescriber (HCP) survey

A target sample size of 40 completed HCP questionnaires is based on statistical and practical considerations. With a sample size around 40, the statistical precision will be approximately ±15%; the precision would increase with larger sample size. It is to be noted that the final survey sample size will depend on HCPs' willingness to participate in the survey. Regardless of the number of respondents, all completed responses received by the cut-off date will be included in the analysis.

Assuming that the response rate could be as low as 10%, at least 400 HCPs will be invited to participate in the survey in order to increase the number of HCPs passing the screening questions and the likelihood that at least 40 HCPs fill out the questionnaire. This estimate is in line with the response rate reported for similar surveys in the literature ([Agyemang et al. 2017](#)).

Patient/Carer survey

A target sample size of 70 patient/carers questionnaires is based on the below practical considerations and assumptions. With a sample size of 70, the statistical precision will be approximately $\pm 12\%$ (see [Table 2](#)).

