Assuming that 15-20% of the targeted 40 HCPs will agree to propose the survey to up to 18 of their patients, a maximum of 144 patients will receive the survey. If approximately 50% of those patients complete the questionnaire, a sample size of 70 patient/carers questionnaires will be reached. HCPs will be reminded to focus efforts on survey distribution to their patients with inhibitors in order to include 25-35 patients with inhibitors or their carers in the target sample size. If a low patient response rate is observed during the course of the study, a second request to HCPs for patient survey distribution will be done if necessary (see [Section 8.4.2](#)).

Although the defined objective is to reach the targeted sample size of 70 completed patient questionnaires, participation is dependent on the HCPs and the patients and their interest in participating in the survey as well as the volume of Hemlibra sold. Every reasonable effort will be made to reach the target patient sample size in this very limited study population.

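### The synopsis and Section 8.5.1 use non-overlapping patient response rates (20-40% and about 50%) for the same target of 70, on an HCP base not updated for version 3

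*Protocol*

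**What the plan says.** The Study Size part of the synopsis (Section 3) opens with the HCP target: "A sample size of 40 HCPs will be surveyed". It adds that at least 400 potential prescribers will be sent the questionnaire. For patients it states "HCPs will be asked to distribute up to 18 survey kits to their patients or carers", and then "Assuming 15-20% of HCPs agree to distribute the survey and that 20-40% of patients/carers respond, our target sample size is 70 patient questionnaires". It does not say which number of HCPs the 15-20% applies to.

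Section 8.5.1 names that base: "Assuming that 15-20% of the targeted 40 HCPs will agree to propose the survey to up to 18 of their patients". It concludes that "a maximum of 144 patients will receive the survey" and continues: "If approximately 50% of those patients complete the questionnaire, a sample size of 70 patient/carers questionnaires will be reached". The same section ties the target to precision: "With a sample size of 70, the statistical precision will be approximately" ±12%.

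Section 8.1, as amended in version 3, widens the group that can hand out kits: "HCPs will be able to propose the online survey to their patients even if they have not participated in the HCPs survey". The version 3 rationale reports 107 completed HCP questionnaires and 46 completed patient questionnaires by 28 July 2020, with data collection extended to the end of December 2020.

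**The concern.** The two sections share a target, an HCP agreement rate and a kit ceiling, but not the patient response rate. The ranges do not overlap: the top of one is 40% and the other is about 50%. The protocol gives no source or reason for either. A reader cannot tell which rate the target rests on, and only the higher one produces 70.

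The calculation also starts from 40 HCPs, although version 3 no longer limits kit distribution to HCPs who took part in the HCP survey. The amendment changed recruitment because patient numbers were short, but left the recruitment arithmetic as it was.

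All analyses are descriptive, so precision is the only statistical basis given for the patient sample size. If the expected n is not supported, neither is the stated ±12%. The planned 25-35 patients with inhibitors are counted within the same 70.

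**Working it through.** **Inputs**
- HCP base: 40 (Section 8.5.1; also the HCP sample size in the synopsis).
- HCPs agreeing to distribute: 15-20% (both sections).
- Kits per distributing HCP: up to 18, a ceiling (both sections).
- Patient response: 20-40% (synopsis) or about 50% (Section 8.5.1).
- Precision: 95% interval with P = 50% (Section 8.5.1).

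**Formula**

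Expected questionnaires = HCP base × share agreeing × kits per HCP × patient response.

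**Step 1: the plan's own figure.** 40 × 0.20 × 18 = 144, the stated maximum. 144 × 0.50 = 72, which agrees with the stated 70. Half-width at 70: 1.96 × √(0.25/70) = 11.7%, which agrees with the stated ±12%.

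**Step 2: both ends of the agreement range.** 40 × 0.15 = 6 HCPs and 6 × 18 = 108 kits; 40 × 0.20 = 8 HCPs and 8 × 18 = 144 kits.

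| Patient response | 108 kits | 144 kits |
|---|---|---|
| 20% (synopsis, low) | 21.6 | 28.8 |
| 40% (synopsis, high) | 43.2 | 57.6 |
| 50% (Section 8.5.1) | 54.0 | 72.0 |

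The synopsis rate gives about 22-58 and the Section 8.5.1 rate gives 54-72.

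**Step 3: what 70 requires on a base of 40.** Response needed: 70/144 = 48.6% at 20% agreement and 70/108 = 64.8% at 15% agreement. Both lie above the synopsis range. At 50% response, 70/0.50 = 140 kits are needed. That is 140/8 = 17.5 of 18 kits for each of 8 HCPs or, with all 18 used, 140/18 = 7.8 HCPs, i.e. 7.8/40 = 19.4% agreement.

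**Step 4: distributing HCPs needed for 70, whatever the base.** With all 18 kits used:
- at 50% response: 70/(18 × 0.50) = 7.8, about 8;
- at 40%: 70/(18 × 0.40) = 9.7, about 10;
- at 20%: 70/(18 × 0.20) = 19.4, about 20.

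These are minimum numbers. If only half the kits are used, each requirement doubles.

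**Step 5: half-widths, 1.96 × √(0.25/n).** n = 70: 11.7%; n = 58: 12.9%; n = 46: 14.4%.

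**Step 6: sensitivity to the HCP base, at the synopsis rates.**
- 107 HCPs (those who had completed the HCP survey): 107 × 0.15 × 18 × 0.20 = 57.8, to 107 × 0.20 × 18 × 0.40 = 154.1.
- 400 HCPs (the minimum invited): 400 × 0.15 × 18 × 0.20 = 216, to 400 × 0.20 × 18 × 0.40 = 576.

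**The case against.** The strongest reply is that Section 8.5.1 closes on its own terms. It calls 144 a maximum, multiplies by about 50% and gets 72. That is right, and the use of the upper limit is disclosed. It does not explain why the synopsis plans the same target on 20-40%.

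A second reply is that 22-58 joins the synopsis response rate to a base that only Section 8.5.1 ties to kit distribution. This also stands as a caution. The synopsis mentions both 40 surveyed and at least 400 contacted HCPs. However, a base of 400 gives 216-576, which fits neither a target of 70 nor a maximum of 144, so 40 is the reading that the protocol supports.

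A third reply is that recruitment is adaptive. Section 8.4.2 provides for monitoring, a second wave, reminders and extra kits. Section 8.5.1 says that participation may limit the number, and Section 8.9 lists sample size as the most important limitation. This limits the consequence but does not reconcile the two rates.

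A reader might infer that 70 cannot be reached, or that precision near ±21% (the half-width at n = 22) is the present outlook. The documents support neither. Version 3 widens the distributing HCPs beyond the 40, a second wave is planned, and 46 patient questionnaires were already in hand with months of collection left. The low end of the 22-58 range has therefore been overtaken.

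**Conclusion.** The inconsistency stands. Two non-overlapping response rates support one target. On the base of 40 HCPs, the synopsis rate falls short of 70 throughout, by about 12 questionnaires at its best (58). The 50% rate reaches 70 only near the top of the agreement range with almost all kits used. The base itself no longer describes the version 3 design.

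The effect on precision is moderate: ±12.9% at 58 and ±14.4% at the 46 already received, against ±11.7% at 70. No hypothesis test, success threshold or analysis method changes, because the study is descriptive. What fails is the planning statement.

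The conclusion assumes that 40 is the intended base in the synopsis, as Section 8.5.1 indicates, and that each distributing HCP uses all 18 kits, which favours the plan. The documents do not show which response rate is correct. The 46 questionnaires do not settle it, because the number of kits handed out is not reported and collection was still open.

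**What to change.** In both the synopsis and Section 8.5.1:

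1. Use one patient response rate and give its justification. Section 8.4.2 has HCPs register kit numbers on a tracking site, so the sponsor should be able to set the 46 questionnaires received against the kits registered. That observed rate should inform the choice.
2. Replace the base of 40 with the contacted HCPs that version 3 allows, and restate the agreement rate for that base. The 15-20% was set for the 40 surveyed HCPs and need not carry over to all those contacted.
3. Show the resulting expected range of n with its half-widths: ±11.7% at 70, ±12.9% at 58, ±14.4% at 46.
4. State the minimum number of distributing HCPs for 70. At 18 kits each this is about 8 at 50% response and 10-20 at 20-40%, and more if fewer kits are used.

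The cost is wording in two places. No procedure or analysis changes. The stated expectation may become less favourable than 70 at ±12%, or the number of distributing HCPs becomes an explicit recruitment target.
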